6.7 Pregnancy

Human chorionic gonadotropin (HCG) serum test will be performed for all women not surgically sterile or at least two years postmenopausal at Screening (Visit 1). An indeterminate reading for the serum pregnancy test should be checked twice (urine test) and discussed with the medical monitor if persistently indeterminant; no study treatment will be administered until this is resolved. HCG urine tests will be performed for all women not surgically sterile or at least two years postmenopausal as per schedule described in [Table 4](#).

Any patient who becomes pregnant during the study will be withdrawn. Patients will be instructed that known or suspected pregnancy occurring during the study, in female patients or female partners of male patients, should be confirmed and reported to the investigator, who will withdraw a pregnant patient from the study without delay and report the pregnancy within 24 hours of first knowledge using a pregnancy report form. The investigator should also be notified of pregnancy occurring during the study but confirmed after completion of the study. In the event that a patient is found to be pregnant after inclusion in the study, any pregnancy will be followed to term, and after delivery, the status of mother and child will be reported to the sponsor after delivery.

Pregnancy is not regarded as an AE unless there is a suspicion that a study treatment may have interfered with the effectiveness of contraceptive medication. Any pregnancy that occurs during study participation must be reported using the same procedures as an SAE ([Section 6.5.1.5](#)).

6.8 Clinical Laboratory Analyses/Evaluations

A laboratory test result that has significantly worsened (according to medical judgment) from Visit 2 result will be recorded on the source documentation, transcribed onto the eCRF as an AE, and monitored as described in [Section 6.5.1.4](#).

Clinical laboratory tests will be performed using a central laboratory, as identified in the Laboratory Procedures Manual provided in the study file documents.

The safety laboratory tests will include:

Haematology: white cell count and differential count, red cell count, hemoglobin, hematocrit, mean cell volume, mean cell hemoglobin, mean cell hemoglobin concentration, platelet count.

Clinical Serum Chemistry: calcium, sodium, potassium, magnesium chloride, bicarbonate or carbon dioxide, glucose, blood urea nitrogen (BUN), creatinine, cholesterol, uric acid, total bilirubin, alkaline phosphatase, gamma glutamyl transpeptidase (GGT), alanine aminotransferase, aspartate aminotransferase, total protein, albumin, lactate dehydrogenase, creatinine phosphokinase (in case of elevated creatinine phosphokinase, the muscle/brain [MB] fraction should be measured), direct bilirubin, indirect bilirubin, prolactin. The prolactin should

be blinded to all the clinical staff, Prilenia Therapeutics and/or its designee. In case of a safety concern, the Investigator will be notified by the central laboratory.

Urinalysis: protein, glucose, ketones, blood (hemoglobin), pH, specific gravity, leukocyte esterase, microscopic (bacteria, red blood cells, white blood cells, casts, crystals). A dipstick urine pregnancy test will be performed as noted in the schedule of assessments ([Table 4](#)).

Patients with CrCL <50 mL/min/1.73 m² calculated using the Cockcroft-Gault equation [(140 - age) × mass (kg) × [0.85 if female] / 72 × serum creatinine (mg/dL)] at any time point after Baseline (Visit 2) will be requested to return to the clinic for an unscheduled visit 1 week later to repeat the CrCL test one more time for confirmation. If the repeated CrCL value is confirmed to be <50 mL/min/1.73 m², the patient will be discontinued from the study treatment.

Any decrease in CrCL that is judged by the investigator as a clinically significant change (worsening) from Baseline (Visit 2) result will be considered an AE, recorded on the source documentation, transcribed onto the eCRF, and monitored as described in [Section 6.5.1.4](#).

However, any clinically significant safety assessments that are associated with the underlying disease, unless judged by the investigator to be more severe than expected for the patient's condition, are **not** to be reported as AEs or SAEs.

6.9 Sample Collections

Blood samples for the determination of laboratory parameters will be collected as per the schedule of assessments ([Table 4](#)) and according to the procedures described in the Laboratory Procedures Manual provided in the study file documents.

Blood samples for the determination of plasma concentrations will be collected at three visits during the study; Visit 4, Visit 6 and Visit 7/ET. Samples will be collected via venipuncture or indwelling catheter in the morning before study treatment administration per the schedule of assessment ([Table 4](#)). Plasma concentration of pridopidine will be measured approximately 1 hour before, and approximately 1 to 2 hours after the PM study treatment dose (approximate C_{max}). When concomitant with ECG recording, PK samples will be collected within 30 minutes after the ECG recording. The timing of UDysRS and UPDRS should be prioritized before PK sampling.

The date and time of each PK sample and the dates and times of the last drug administration prior to any collected PK sample will be recorded on the source documentation and transcribed onto the eCRF. Only major deviations (>5%) from the scheduled blood sampling time points will be commented on the respective page of the eCRF.

Samples will be analyzed by [REDACTED] using an appropriate validated method for pridopidine and its main metabolite TV-45065.

Blood samples for DNA extraction will be collected only once during the study at Screening (Visit 1) or at Baseline (Visit 2). Plasma samples for potential biomarkers research will be collected at the time points noted in the schedule of assessments ([Table 4](#)). The details of the sample collection and handling are described in the Laboratory Procedures Manual provided in the study file documents.

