3.1.6 Pharmacokinetics

PK sampling for levels of pridopidine and its metabolite TV-45065 will be performed at the time points noted in the schedule of assessments ([Table 4](#)) (approximately 1 hour before and 1 to 2 hours after the PM pridopidine dose). When coincident with ECG monitoring, PK samples will be collected within 30 minutes after the ECG recording.

Details of all PK assessments performed during the study are provided in [Section 6, Table 4](#).

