Abbreviations: PD, Parkinson's disease; PD-LID, levodopa-induced dyskinesia in patients with Parkinson's disease; SNRI, serotonin-norepinephrine reuptake inhibitor; SSRI, selective serotonin reuptake inhibitor;

^a Due to either QT prolongation effects or metabolism by CYP2D6 into active metabolites

** Fluoxetine is allowed as it carries a conditional risk only for patients with congenital Long QT, hypokalemia or metabolic inhibitors.

Other:

- Use of all oral cannabinoids (including all preparations containing any cannabinoids, including cannabidiol, as well as prescribed oral medical marijuana and oral cannabidiol) with only an exception for topical formulations of cannabidiol, are prohibited within 28 days prior to Baseline (Visit 2) and during the study
- Amantadine is not allowed within 4 weeks prior to the UDyRS Part 4 assessment for eligibility, concordance testing, and completion of the 3 consecutive 24 hour "ON/OFF" home diaries during the screening period
- Apomorphine is not allowed within 28 days prior to screening and during the study

6 Study Assessments and Procedures

Before performing any study procedures, all potential patients will sign an IRB-approved- ICF. Patients will have the opportunity to have any questions answered before signing the ICF. The investigator must address all questions raised by the patient. The investigator or designee will also sign the ICF.

On-site (in-clinic) visits should be scheduled around the second (PM) study treatment daily dose within the time window of 11:00 AM through 5:00 PM and at consistent time points. Attempts will be made to schedule all study visits for an individual patient at approximately the same time of the day. The same in-clinic procedural timing will be kept for each of the in-clinic- visits for each patient. The in--clinic procedural flow for Baseline (Visit 2) is presented in [Appendix 13.1](#). The in-clinic procedural flow for Visits 3 to 7 is presented [Appendix 13.2](#). The second (PM) study treatment daily dose (at clinic) should be taken 6-10 hours after the first (AM) study treatment daily dose, which is taken at home, and not later than 5:00 PM.

A detailed schedule of study procedures/assessments is provided in [Table 4](#).

Table 4 Schedule of Assessments

Study Period ^a	Screening		Treatment Period							Down-titration	Safety Follow-Up
			Up-titration		Maintenance						
Study Week			Week 1 ^b	Week 5	Week 7	Week 10	Week 13	Week 16/ET ^c	Week 17 ^d	Week 18	

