- y. Investigators must complete a detailed case note at Visit 2 to document the patient’s condition before starting study drug. This will be the baseline in which to compare changes in the patients’ global condition after receiving study drug for rating the CGI-C.
- z. During the 16-week active treatment period, the first study treatment daily dose will be taken between 6:00 and 8:00 AM and the second study treatment daily dose will be taken 6 to 10 hours after the first study treatment dose administration and not later than 5:00 PM. The second study treatment daily dose should be taken 0 to 120 minutes BEFORE the “scheduled levodopa dose” (NOT after). As much as possible, study treatment should be taken at the same

time throughout the study. Capsules will be swallowed whole with water. Study treatment can be taken irrespective of meals. If a patient misses the morning study treatment dose on an in-clinic day, the visit should be rescheduled.

- aa. Study treatment kit for down-titration purposes. At the end of the maintenance period or at ET, active treatment patients will undergo a down-titration period in which they will receive one capsule of pridopidine 75 mg and one capsule of placebo BID on Days 1 to 2 followed by one capsule of pridopidine 75 mg and one capsule of placebo QD on Days 3 to 4 of Week 15. Patients receiving placebo will receive matching placebo at the same dosing schedule as patients assigned to the active treatments.
- bb. Pharmacokinetic sampling will be performed at Visit 4, Visit 6, and Visit 7/ET approximately 1 hour before and 1 to 2 hours after the PM study treatment dose. When concomitant with ECG recording, PK samples will be collected within 30 minutes after the ECG recording. The timing of UDysRS and UDPRS should be prioritized before PK sampling.
- cc. Sampling analyses for DNA extraction will be performed only once during the study at the Screening (Visit 1) or at Baseline (Visit 2).
- dd. Sampling analyses will be performed at Screening (Visit 1) or Visit 2, Visit 5, and Visit 7/ET.
- ee. If a patient misses the morning study treatment dose on an in-clinic day, the visit should be rescheduled.

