## 16 Analysis of PK

Plasma concentrations of pridopidine and its metabolite TV-45065 will be summarized with descriptive statistics by visit and timepoint (1 hour before and 1 to 2 hours after the pridopidine dose). The relationship between plasma concentrations of pridopidine and TV-45065 versus the primary endpoint (and the change from baseline in the primary endpoint) may be explored graphically for each visit which include both the PK and primary efficacy assessments. Separate exploration may be conducted for the PK assessments conducted before and 1 to 2 hours after the pridopidine dose.

PK analyses will be performed after the study database is locked, the study unblinded only if they are deemed necessary. Otherwise, PK data will only be included in listings, if there is not much data for analysis.

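### Protocol 6.9 describes a morning, pre-treatment PK draw that conflicts with the PM-dose sampling schedule in 6.9 itself, 3.1.6 and Table 4, and SAP 16 does not resolve it

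*Protocol*

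**What the plan says.** Protocol 6.3 refers the reader to 6.9 for PK sample collection. For Visits 4, 6 and 7/ET, 6.9 first states: "Samples will be collected via venipuncture or indwelling catheter in the morning before study treatment administration", with a pointer to Table 4. Its next sentence sets the concentrations at "approximately 1 hour before, and approximately 1 to 2 hours after the PM study treatment dose".

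Two other places give only the PM timing:

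- Protocol 3.1.6: "approximately 1 hour before and 1 to 2 hours after the PM pridopidine dose".
- Table 4 footnote bb: "approximately 1 hour before and 1 to 2 hours after the PM study treatment dose".

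The clinic-day rules bear on whether a morning draw is feasible. Table 4 footnote z puts the first daily dose at 6:00–8:00 AM. Protocol section 6 places visits at 11:00 AM to 5:00 PM and times the PM dose 6–10 hours after "the first (AM) study treatment daily dose, which is taken at home, and not later than 5:00 PM". Table 4 footnote ee adds: "If a patient misses the morning study treatment dose on an in-clinic day, the visit should be rescheduled".

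SAP 16 summarises concentrations "by visit and timepoint (1 hour before and 1 to 2 hours after the pridopidine dose", without saying which daily dose is meant. It makes the PK analysis conditional, with listings as the fallback.

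**The concern.** Two consecutive sentences of the controlling section give different sampling times. A site that took the first at face value, as a draw before the day's first dose, would collect an overnight trough in place of the mid-interval sample that the rest of the protocol asks for.

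The two samples belong to different dosing intervals and are not interchangeable. SAP 16 has a single pre-dose label and no rule for placing a sample by its actual time. If any such draws occurred, they could enter the same pre-dose summary, and the same pre-dose exposure-response plot, as correctly timed ones. Exploring exposure against dyskinesia is a stated PK objective in both documents, and SAP 16 foresees a separate look at the pre-dose samples.

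**Working it through.** **Step 1. Can any reading satisfy all the passages?** The 6.9 sentence governs the PK samples generally, and two are scheduled per visit.

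- Post-dose sample: drawn 1–2 h after the PM dose, so it is never in the morning before a dose. No reading of the phrase covers it.
- Pre-dose sample, read as before the AM dose: the draw must precede a dose taken at home at 6:00–8:00 AM. The clinic window opens at 11:00 AM, at least 3 h later (11:00 − 8:00). Drawing in clinic would mean withholding the AM dose, and a missed AM dose triggers rescheduling.
- Pre-dose sample, read as before the PM dose: possible only if the draw falls before noon, that is, if the PM dose is taken before 13:00.

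**Step 2. Clock arithmetic from the protocol's dosing rules.** Inputs: AM dose 6:00–8:00; PM dose 6–10 h later and not after 17:00.

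| Quantity | Calculation | Result |
|---|---|---|
| PM dose | earliest 6:00 + 6 h; latest 17:00 | 12:00–17:00 |
| Intended pre-dose draw | PM dose − 1 h | 11:00–16:00 |
| Intended draw, time since AM dose | (6 to 10 h) − 1 h | 5–9 h |
| Post-dose draw | PM dose + 1 to 2 h | 13:00–19:00 |
| Pre-AM draw, time since previous PM dose | 17:00 to 6:00; 12:00 to 8:00 | 13–20 h |

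**Step 3. Size of the difference, under assumptions.** The plan states no figure to reproduce and gives no half-life. Assume a one-compartment model at steady state, first-order absorption at 1.5/h, half-lives of 5, 8, 10 and 15 h, equal doses at fixed clock times, and a pre-AM draw 0.1 h before the dose.

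Let k = ln 2 / half-life, and let g be the hours from AM to PM dose. At 5 h or more after a dose the absorption term is negligible (e^(−1.5×5) ≈ 0.0006). The steady-state factor 1/(1 − e^(−24k)) cancels. Hence

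ratio (pre-AM / pre-PM) = [e^(−23.9k) + e^(−(23.9−g)k)] / [e^(−(g−1)k) + e^(−23k)]

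Example with g = 7 (07:00 and 14:00) and half-life 10 h, so k = 0.0693: (0.191 + 0.310) / (0.660 + 0.203) = 0.501 / 0.863 = 0.58.

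| g (h) | t½ 5 h | t½ 8 h | t½ 10 h | t½ 15 h |
|---|---|---|---|---|
| 6 | 0.22 | 0.43 | 0.53 | 0.68 |
| 7 | 0.28 | 0.49 | 0.58 | 0.72 |
| 10 | 0.55 | 0.72 | 0.77 | 0.85 |

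Over the allowed gaps the ratio runs from 0.22 to 0.85. The pre-AM sample would be 15% (1 − 0.85) to 78% (1 − 0.22) below the intended one, or roughly 15–80%.

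This models a draw just before an AM dose at its usual time. A clinic draw after withholding the AM dose would come at least 18 h after the previous PM dose (17:00 to 11:00) and would be lower still.

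**The case against.** The best defence is that the sentence does not stand alone. It defers to Table 4, whose footnote bb fixes the timing to the PM dose, and the next sentence of 6.9 says the same. A site reading the whole paragraph would probably sample correctly. The dose given in clinic is the PM dose, so the phrase may only be a loose description of a late-morning draw before it. With a PM dose at 12:00 the pre-dose draw is at 11:00 AM; SAP 4.2 puts the afternoon dose at 1:00 PM ± 1 h, which gives a draw at 11:00–13:00.

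This stands in part. A reader might infer that any literal 6.9 draw is an overnight trough; the late-morning reading shows that it need not be. That reading still fails for PM doses from 13:00 onward and for every post-dose sample, so the contradiction remains.

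A reader might also infer that samples from different sites will be pooled under one label, or that sites will withhold the AM dose and so alter exposure at the UDysRS and ECG that day. The documents do not support either as an expected outcome. The home AM dose, the visit window and the reschedule rule all work against it.

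Safeguards exist too. Sample and last-dose times go into the eCRF, and timing deviations above 5% are commented. These make mis-timed samples identifiable. But the comment rule cannot say which of two conflicting schedules is the reference, and SAP 16 does not say how the recorded times are to be used.

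Finally, SAP 9.3 reports that the study stopped before 30 subjects were enrolled, so correcting the protocol text now has little prospective value.

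**Conclusion.** The contradiction is real. The morning phrase in Protocol 6.9 conflicts with its own next sentence, 3.1.6 and Table 4 footnote bb, and no reading reconciles it with the two-sample schedule.

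SAP 16 should not be read as requiring PM sampling. It refers only to the pridopidine dose, so it neither contradicts 6.9 nor settles the question. Mislabelling a pre-AM draw as the one-hour-before sample is possible under the plan as written, but not shown to be likely.

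The clock gaps (13–20 h against 5–9 h) follow from the protocol's own rules. The 15–80% shortfall rests on the assumed kinetics and half-lives. A narrower figure of about 30–70% would hold only for doses at 07:00 and 14:00.

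The effect is confined to PK summaries and exploratory exposure-response plots, which may be reduced to listings. No efficacy result, sample size or error rate depends on it.

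**What to change.** In Protocol 6.9, reconcile the text with 3.1.6 and footnote bb by removing the phrase about a morning draw before study treatment, leaving the PM-dose timing already in the next sentence.

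In SAP 16:

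- Name the PM dose as the reference for both time points.
- Assign each concentration to a time point from the sample and last-dose times already recorded in the eCRF.
- List separately, outside the one-hour-before summary, any sample not drawn in that interval.

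Because enrolment has ended, the SAP change is the more useful half. The cost is one deleted phrase and one or two SAP sentences, with no new samples or data fields. The downside is that a few mis-timed samples, if there are any, leave an already small summary.

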6.10 Eligibility Review

An eligibility review will be conducted by the EAC to determine suitability of screened subjects for the study, including review of screening safety data and fulfillment of enrollment criteria. Screened subjects will be reviewed within 48 hours of potential randomization to ensure that they meet the criteria for enrollment.

7 Statistical and Analytical Plan

Details of the statistical analyses, methods, and data conventions will be described in the statistical analysis plan (SAP), which will be approved before breaking the blind of the study.

Primary and all secondary endpoints will be assessed for both the 100 mg BID and the 150 mg BID pridopidine dosage vs. placebo in a hierarchical manner.

7.1 Primary Efficacy Endpoint

The primary endpoint is the mean change from Baseline (Visit 2) to Visit 7/ET in the sum of Parts 1, 3, and 4, of the UDysRS while the patient is in the peak “ON” state and judged to be experiencing peak dose dyskinesia.

7.2 Secondary Efficacy Endpoints

The following secondary endpoints will be evaluated:

1. Mean change from Baseline (Visit 2) to Visit 7/ET in “ON time without troublesome dyskinesia” based on “ON/OFF” home diary completed by the patients during three consecutive 24-hour intervals
2. Mean change from Baseline (Visit 2) to the end of Visit 7/ET in the total UDysRS score (Parts 1 to 4)
3. Proportion of patients improving based on PGI-C at Visit 7/ET
4. Mean change from Baseline (Visit 2) to Visit 7/ET in “ON time without any dyskinesia” based on “ON/OFF” home diary
5. Proportion of patients improving based on CGI-C at Visit 7/ET
6. Mean change from Baseline (Visit 2) to Visit 7/ET in the score of UPDRS Part 2
7. Proportion of responders (improvement in dyskinesia and no worsening in motor function) at Visit 7/ET. The improvement in dyskinesia is defined as $\geq 30\%$ improvement in UDysRS score (Parts 1, 3, and 4) from Baseline (Visit 2) and no worsening from Baseline (Visit 2) in “OFF” which is defined as ≤ 30 minutes increase in “OFF” time from Baseline (Visit 2) per a 24 hours period
8. Mean change from Baseline (Visit 2) to Visit 7/ET in “OFF time” based on “ON/OFF” home diary
9. Mean change from Baseline (Visit 2) to Visit 7/ET in the UPDRS Part 3 as measured immediately prior to the in-clinic L-DOPA dose

7.3 Safety Endpoints

The following safety and tolerability endpoints will be evaluated:

Safety:

1. AEs occurring throughout the study
2. QTc parameters: absolute QTcF of >450 msec, >480 msec, and >500 msec, mean QTcF, change in QTcF >30 msec and <60 msec, or changes in QTcF >60 msec throughout the study
3. Clinical safety laboratory (clinical chemistry, haematology and urinalysis, vital signs (including assessment of orthostatic hypotension), physical and neurological examination, concomitant medications throughout the study
4. Change from Baseline (Visit 2) in suicidality as evaluated with the C-SSRS throughout the study
5. Change from Baseline (Visit 2) in impulse control disorder (ICD) as evaluated by the QUIP-RS throughout the study

Tolerability:

1. The number (%) of patients who complete the study treatment
2. The number (%) of patients who fail to complete the study treatment due to AEs
3. The number (%) of patients who fail to complete the study treatment due to QTcF and QT stopping rules, seizure or convulsions ([Section 4.2.1](#))

7.4 Pharmacokinetic Endpoints

The PK measure will be the determination of plasma concentration of pridopidine and its metabolite TV-45065 before and after in-clinic pridopidine dose.

7.5 Pharmacogenetic and Plasma Biomarker Endpoints

The following pharmacogenetic and plasma biomarker endpoints may be evaluated:

1. To analyze the correlation of potential genetic variations and plasma biomarkers with clinical treatment responses to study drug (e.g., efficacy, PK, tolerability and safety features).
2. To assess for potential genetic variation and plasma biomarkers associated with disease progression and severity.

